During the initial screening process, potential subjects will be asked to provide a urine specimen that will be screened for the presence of amphetamine, benzodiazepines, barbiturates, COC, tetrahydrocannabinol (THC) and opiates. In order to participate in an experimental session, subjects must provide a urine negative for amphetamine, barbiturates, benzodiazepines and opiates on each day of their participation. Subjects will be allowed to continue if they test positive for COC, if it is determined that this drug was given in a recent session and it is likely that the result is positive due to experimental administration. [name] or [name] will be notified of COC-positive urines on experimental session days and sessions will only proceed if subjects pass the sobriety test and have vital signs within acceptable limits (see below). Subjects will be maintained on a caffeine free diet and will have to abstain from alcohol for the duration of their participation.

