## 7. RESEARCH PROCEDURES

*General Procedures.* Subjects that meet the inclusion criteria will participate as inpatients at the University of Kentucky CCTS Research Inpatient Unit (CRIU). Subjects will be discharged upon completion of the entire protocol.

This experiment will require each subject to participate for approximately five weeks. Experimental sessions will be conducted as outlined in Table 1 below. We would like to note that COC doses will both be given in random order, whereas order of PHEN dosing will be counterbalanced across subjects. We would also like to note that subjects may be maintained on a given PHEN condition for more than 11 days prior to session to avoid testing COC doses on weekends.

Day	Table 1. Experimental Procedures
1	Admission to the CRIU.
2	Practice Session.
3-17	Placebo maintenance. Placebo administered twice daily (0700 and 1900 hours).
14-17	Experimental Sessions. Reinforcing effects of intranasal COC (0 [placebo], 20, 40 and 80 mg) determined using progressive-ratio procedure.
18-32	PHEN maintenance. Administered in divided doses (0700 and 1900 hours). Subjects receive 35 mg twice daily for two days, then 70 mg twice daily for two days, then 105 mg twice daily for remainder of maintenance period.
29-32	Experimental Sessions. Reinforcing effects of intranasal COC (0 [placebo], 20, 40 and 80 mg) determined using progressive-ratio procedure.
33	Discharge

During their participation in the research protocol, subjects will not be allowed to leave the CRIU, nor will visitors be allowed, with the exception that subjects can leave for walks under clinical supervision and if approved by physicians. Research subjects will be allowed to make local telephone calls. After completing the research protocol, interested subjects will be offered a referral to an appropriate drug abuse treatment program.

All subjects will provide urine and expired air samples before and periodically during study participation. The presence of non-nicotine drugs of abuse or alcohol not administered experimentally in the research protocol will result in immediate termination from the research study.

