This experiment will consist of 1 practice session and 8 experimental sessions conducted according to the timeline in Table 1 (see above). After admission, subjects will be allowed to acclimate to the CRIU for two days before beginning the study. During this time, subjects will be maintained on a caffeine-free diet, receive instructions concerning the details of the daily research procedures and general rules of the inpatient research unit and complete a "practice" session to familiarize them with the experimental routine and tasks.

Each day after the practice session, subjects will be awakened at 0700 hours and will receive maintenance medication. Medications will not be administered if a subject's heart rate is  $\geq 100$  bpm, systolic pressure is  $\geq 150$  mmHg or diastolic pressure is  $\geq 100$  mmHg. In addition, the UKU side effects scale will be completed daily to monitor for the emergence of side effects.

Subjects will then be allowed to eat a standard, fat-free breakfast (cereal with skim milk, 2 pieces of toast with jam or jelly and 8 ounces of fruit juice). Tables 2 and 3 (below) outline the activities of maintenance and experimental sessions. The sampling of each session will begin at 0900 hours and will last approximately 1 hour. Self-administration phases will begin at 1330 hours and will last approximately 2 hours. Experimental measures will be completed as outlined in Tables 2 and 3 below. Medications will not be administered if a subject's heart rate is  $\geq 100$  bpm, systolic pressure is  $\geq 150$  mmHg or diastolic pressure is  $\geq 100$  mmHg or if clinically significant and/or prolonged ECG abnormalities are detected.

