Subjects will be excluded from further research participation if at any time during the experimental sessions COC increases heart rate above 130 bpm, systolic pressure above 180 mmHg, diastolic pressure above 120 mmHg or if clinically significant and/or prolonged ECG abnormalities are noted. Subjects will remain seated for the duration of the experimental session. Between the sampling and self-administration phases, subjects will be allowed to eat a standard hospital lunch but will not be allowed to smoke. No experimental activities will be scheduled for the remainder of the day after a self-administration session, but subjects will receive their appropriate maintenance medication at 1900 hours. Subjects will be free to engage in recreational activities (e.g., watch television, read, listen to music, arts and crafts, play video or board games). Research subjects will be required to be in bed with the lights out by 2300 hours.

Time	Table 2-Daily Activities for Maintenance Days
0700	Patient awakened. Vital signs recorded. Medication administered if vitals are within range and no indication of sedation or withdrawal. Subject eats breakfast.
1200	Lunch is served.
1300	UKU completed.
1900	Dinner is served. Vital signs recorded. Medication administered if vitals are within range and no indication of sedation or withdrawal.
2300	Lights out.

Time	Table 3-Daily Activities for Experimental Days
0700	Patient awakened. Vital signs recorded. Medication administered if vitals are within range and no indication of sedation or withdrawal. Subject eats breakfast.
0900	Vital signs recorded. Computerized tasks completed. ECG monitoring begins.
0930	Vital signs recorded. 0 [placebo], 20, 40 or 80 mg intranasal COC administered if vitals are within range. Measures completed 0, 15, 30, 45 and 60 minutes after drug administration.
1030	Sampling phase ends.
1200	Lunch is served.
1300	UKU is completed.
1330	Vital signs recorded. Computerized tasks completed (including progressive-ratio task). ECG

	monitoring begins.
1430	Vital signs recorded. Portion of intranasal dose earned is administered if vitals are within range. Measures completed 0, 15, 30, 45 and 60 minutes after drug administration
1530	Session ends. Remainder of daily activities identical to those listed in Table 2.

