**Self-Administration Phase.** Four hours after sampling the available COC dose, participants will complete the Self-Administration Phase. During the Self-Administration Phase, participants will be given up to 10 opportunities to earn 1/10 of the dose of COC dose insufflated during the Sampling Phase or \$0.25. Before the Self-Administration Phase, participants will be instructed that the total amount of drug/money earned will be administered after completing the entire progressive-ratio procedure. Participants must choose one of the two options at each of the 10 opportunities. Participants will be able to earn drug doses or money by responding on a computer mouse according to a progressive-ratio schedule. The ratio for the first choice will be 400 clicks. The response requirement will increase by 100 for a selected option (i.e., 500, 600, 700, 800, 900, 1000, 1100, 1200, 1300 responses if the subject exclusively chooses drug or money). We have conducted several experiments in recent years designed to refine human drug self-administration procedures to enhance our ability to determine the initial efficacy of potential pharmacotherapies for stimulant dependence (Sevak et al., 2010; [name] et al., 2011). The results of ongoing experiments that used progressive ratio procedures nearly identical to those proposed in this application suggest that the reinforcing effects of oral and intranasal stimulants are an orderly function of dose (Marks et al., Under Review; Pike et al., 2014; [name] et al., 2012a). Previous studies have also shown that the reinforcing effects of COC are amenable to pharmacological manipulation under a similar arrangement (Greenwald et al., 2010; [name] et al., 2012a).

**Subjective Questionnaires.** A battery of subjective questionnaires will also be used to assess drug effects. These measures have previously been shown to be sensitive to the effects of stimulants ([name] et al., 2009). These experimental measures will be taken on all experimental session days. The measures described below will be recorded as described in the tables above. The subjective effects measures are included in Appendix A.

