**Vital Signs.** Heart rate, blood pressure, oral temperature and heart rhythmicity (via ECG) will be recorded using a Dinamap digital monitor (Critikon, Pro 1000, Tampa, FL). These measures will be completed at as described in the tables above. Telemetry-certified nurses will interpret the results of the ECG with instructions to contact Drs. [name] or [name] regarding abnormalities.

**Performance Task.** Psychomotor performance will be assessed at the same time as subjective drug-effects during all sessions with a computerized version of the Digit-Symbol-Substitution Test (DSST) (McLeod et al., 1982). In this procedure, the subject uses a numeric keypad to enter a geometric pattern displayed on a video screen. Subjects will have 90 seconds to enter as many geometric patterns as possible. The dependent measures are the number of geometric patterns the subject attempted to enter and the number of patterns entered correctly. This task will be completed immediately following the subjective questionnaires.

**Drug Dose and Administration.** All drugs will be administered under double-blind conditions and under medical supervision. COC doses will be given in random order. PHEN doses will be given in counterbalanced order across subjects. Doses of COC HCl will be prepared by weighing out the appropriate amount of powdered COC. The powder will then be mixed with lactose monohydrate powder, N.F. to make a total of 100 mg powder. Placebo will be prepared in an identical fashion, but will contain only lactose monohydrate powder. Doses of COC will be prepared individually for each subject. Doses of 0 [placebo], 20, 40 and 80 mg intranasal COC will be placed into individual glass vials labeled for each subject for each sampling session. Doses of PHEN (0, 35, 70 and 105 mg, administered two times daily) will be prepared by over-encapsulating commercially available tablets in a size 0 capsule. The capsule will then be loose filled with cornstarch. Placebo capsules will be prepared in an identical fashion, but will contain only cornstarch.

**Data Analysis.** Data will be analyzed as raw scores. Statistical significance refers to  $p \leq 0.05$ .

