Progressive-ratio data (i.e., break point, number of COC doses earned) will be analyzed with two-factor mixed-model ANOVA with COC (within-subject variable; 0 [placebo], 20, 40 and 80 mg), and PHEN (within-subject variable; 0 and 210 mg/day) as the factors. A significant attenuation (i.e., rightward shift in the dose response) of the effects of COC will be inferred if the main effect of PHEN or the interaction of COC and PHEN attains statistical significance in the ANOVA. If the COC-PHEN interaction attains statistical significance, the mean square error term will be used to conduct Tukey's HSD *post-hoc* test to make appropriate pair-wise comparisons between means. Peak-effect and AUC data for the cardiovascular, performance and subjective effects measures obtained during the sampling phase will be analyzed in a similar fashion. Cardiovascular, performance and subjective effects data from the self-administration phase will not be analyzed because participants will likely ingest varying amounts of COC making these data difficult to interpret.

The primary outcome measures for this study are the break point and number of COC doses earned on the progressive-ratio procedure in subjects maintained on active PHEN or placebo. Considering the complete within-subject design, number of dose levels of each drug (i.e., two PHEN conditions and four doses of intranasal COC) enrolling 36 subjects will provide adequate power to detect an effect size ( $d$ ) of at least 0.44 for attenuation of the reinforcing effects of COC as a function of maintenance on PHEN and placebo ( $\text{power} = 0.80$ ,  $\alpha = 0.05$ , G\*Power). We used the results of a previous study conducted in our laboratory to determine an appropriate sample size for the present experiment ([name] et al., 2010). That study demonstrated that d-amphetamine maintenance decreased the reinforcing effects of COC with an estimated effect size ( $d$ ) of approximately 0.46.

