## **15. PAYMENT**

Subjects will be paid \$40 for each day they reside on the CRIU and will receive a \$40 completion allowance for these days if they complete the entire experiment. Subjects can also earn an additional \$2.50 during each experimental session depending on how they distribute choices for drug and money. Any money earned in experimental sessions will be added to their overall payment. The amount earned by the subject will be disbursed to them upon completion of the study. Payments will be disbursed in amounts up to \$500 dollars and will be given once per week following discharge until the subject is paid in full. When subjects return on a weekly basis to receive their payments, we will survey them regarding

their drug use since being discharged from the study. A subject can earn approximately \$2660 for participating in this study.

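### Does a sampling dose withheld on vital signs leave the primary progressive-ratio analysis without a usable rule?

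*Combined protocol and SAP*

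**What the plan says.** All of this is in the combined protocol and SAP.

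- **Primary analysis (section 7, Data Analysis).** "Progressive-ratio data (i.e., break point, number of COC doses earned) will be analyzed with two-factor mixed-model ANOVA with COC" (four doses) and PHEN (two conditions) as within-subject factors, giving eight cells per person. If the interaction is significant, Tukey's HSD follows, using the ANOVA mean square error.
- **Check before the sampling dose (section 7, Table 3, 0930).** "0 [placebo], 20, 40 or 80 mg intranasal COC administered if vitals are within range". The general rule in the same section begins "Medications will not be administered if a subject's heart rate is" and sets limits of 100 bpm, 150 mmHg systolic and 100 mmHg diastolic, plus ECG abnormalities. Section 4 adds, for session days with a COC-positive urine, that "sessions will only proceed if subjects pass the sobriety test and have vital signs within acceptable limits".
- **Link to the primary outcome (section 7, Self-Administration Phase).** "participants will be given up to 10 opportunities to earn 1/10 of the dose of COC dose insufflated during the Sampling Phase", or money.
- **Schedule (section 7, Table 1).** Each maintenance condition has four session days: "Experimental Sessions. Reinforcing effects of intranasal COC (0 [placebo], 20, 40 and 80 mg) determined using progressive-ratio procedure".
- **Numbers.** Section 4 aims for 36 completers from up to 100 screened. Section 3 has every subject receive every dose condition. Section 7 sets eight experimental sessions. Section 15 pays a "completion allowance for these days if they complete the entire experiment". Section 17 combines the data of all subjects for analysis.

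The documents give no analysis set, no empty-cell rule and no table of withheld doses by maintenance condition.

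**The concern.** If no dose is insufflated in the morning, the afternoon reinforcer is undefined and that session has no valid break point or count of doses earned. Withholding does not end participation, so someone could reach discharge with fewer than eight cells. Section 9 lists changes in heart rate and blood pressure as side effects and says side effects may be more frequent and larger on the combination. Losses could therefore fall mainly on PHEN.

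The analysis wording points two ways. Mixed-model ANOVA suggests using every available session, while Tukey's HSD from a single mean square error suits equal cell counts. Two analysts could test different numbers of people. Dropping everyone with a gap could cost power.

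The tolerability hypothesis in section 1 is also touched. The planned cardiovascular comparison uses sampling-phase peak and AUC, where "Data will be analyzed as raw scores", and sessions stopped for high vital signs do not contribute.

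**Working it through.** **1. The plan's own figure.** The plan states 36 people, d = 0.44, power 0.80 and alpha 0.05. A paired t-test (noncentral t) needs 34 people one-sided (power 0.83 at 36) and 43 two-sided (power 0.73 at 36). The plan does not state sidedness. Below, 0.80 at 36 is taken at face value.

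**2. Is a value necessarily lost?** Nothing says the afternoon phase is cancelled after a withheld sampling dose, and Table 3 puts no vital-sign condition on the 1330 task. The session might be skipped, run or repeated. The second check, at 1430, comes after the task, so it cannot remove break point or doses earned.

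**3. Are make-up days ruled out?** The payment arithmetic is 33 × ($40 + $40) + 8 × $2.50 = $2,660, which matches section 15. That total is stated as approximate, pay accrues per resident day, and section 7 allows longer maintenance to avoid weekend testing. Those permitted extra days are not in the 33 either. The total therefore does not show that make-up days are excluded.

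**4. Size without a blood pressure model.** With chance q of losing any one session, independently, the expected number with all eight cells is 36 × (1 − q)^8:

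| q | complete people of 36 |
|---|---|
| 1% | 33.2 |
| 2% | 30.6 |
| 5% | 23.9 |
| 10% | 15.5 |

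This matters only if people with gaps count towards the 36 and are then dropped.

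**5. Size with an assumed model.** All inputs are assumptions except the 150 mmHg limit. Pre-dose systolic = mean + b + d (on PHEN) + e, with b ~ N(0, 11²), d ~ N(10, 6²) and e ~ N(0, 7²). The dose is withheld at 150 or above.

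- Complete-case power = Φ(2.802 × √share − 1.960), where share is the fraction with all eight cells and 2.802 = 1.960 + 0.842.
- All-available power replaces share with the mean of (1/(1/n0 + 1/n1))/2, where n0 and n1 are the dosed sessions out of four in each condition.

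| Mean systolic (mmHg) | 115 | 120 | 125 | 130 |
|---|---|---|---|---|
| Withheld, placebo maintenance | 0.4% | 1.1% | 2.8% | 6.3% |
| Withheld, PHEN | 4.1% | 8.2% | 14.8% | 24.3% |
| Complete people of 36 | 32.6 | 29.7 | 25.6 | 20.5 |
| Complete-case power | 0.76 | 0.72 | 0.66 | 0.56 |
| All-available power | 0.79 | 0.77 | 0.75 | 0.70 |

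**6. Do the right-hand columns fit the eligibility rules?** Section 10 screens out hypertension. With SD 11, the share with usual systolic of 140 or more is 1 − Φ((140 − 125)/11) = 9% at mean 125 and 1 − Φ((140 − 130)/11) = 18% at mean 130. The documents give no cut-off. Taking 140 as an assumed one and truncating b there:

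| Mean before truncation (mmHg) | 115 | 120 | 125 | 130 |
|---|---|---|---|---|
| Complete people of 36 | 32.9 | 30.7 | 27.8 | 24.8 |
| Complete-case power | 0.76 | 0.74 | 0.69 | 0.64 |
| All-available power | 0.79 | 0.78 | 0.77 | 0.76 |

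All-available power stays within about 0.04 of plan.

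**7. The completer reading.** Taking sections 3, 4, 7 and 15 together, a completer is someone with all eight sessions, and recruitment runs until there are 36. That gives 36 × 8 = 288 filled cells. Counts are then equal, Tukey's HSD from one mean square error fits, and power is as planned.

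**The case for a change.** The strongest counter-argument is that the gap lies in the primary outcome and the plan leaves the analyst to choose. Complete-case deletion from a fixed 36 would cost real power even after truncation (0.64 at the highest assumed mean). That outcome needs an analyst to count people with gaps towards the 36 and then discard them, which neither natural reading of the plan does.

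A second argument has more substance. The planned cardiovascular comparison covers dosed sessions only. Under the untruncated model with a 10 mmHg effect, a simulation put the understatement of the PHEN difference in peak systolic pressure at about 5, 11, 17 and 28% across the four assumed means, even with a mixed model. With no PHEN effect there is no such bias. The larger figures come from the columns that sit badly with the hypertension screen. The evidence on tolerability is also wider than this comparison: vital signs are recorded before the dose on every session day, the UKU scale is completed daily, and adverse events are documented and reviewed weekly. The point stands as a caution in reading that comparison.

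On likelihood, section 9 is mixed. It expects possibly larger effects on the combination but also calls side effects unlikely at these doses. Sections 1 and 7 report that COC was given safely during PHEN at 210 mg/day and that this dose was well tolerated.

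**Conclusion.** The omission is real, but it is missing detail and not a fault in the analysis. Using all available sessions and defining completers as people with all eight sessions are both sensible and consistent with the text, and neither produces a serious loss of power under plausible assumptions. All-available power is 0.76 to 0.79 against 0.80, assuming a 10 mmHg PHEN effect, between- and within-person SDs of 11 and 7, no usual systolic pressure of 140 or more, and the systolic limit alone. The heart-rate and diastolic limits would add to withholding. The model also ignores that PHEN itself is withheld at the same limits, so actual rates could differ either way. The documents give no withholding rate, so the true size is unknown. A fall in power to 0.56 and the absence of make-up days are not established. No bias in the primary estimate is claimed. Setting out the rule would mostly record what an analyst would do anyway, and extra safety tables would be optional. No change to the plan follows.

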## **3. STUDY DESIGN**

A double-blind, placebo-controlled, crossover design will be used in this experiment. A completely within-subject design will be used such that each subject will receive all possible dose conditions, including placebo.

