## **17. DATA AND SAFETY MONITORING**

### *Data Monitoring Plan*

Data will be collected using a computerized data collection and management system wherever possible. This system automates the collection of data, which ensures the accuracy and completeness of data collection. The data are stored in a unique file on the hard drive of the computer and are printed after all the tasks are completed. In all instances, the data files do not contain the name of the subject, but instead, each subject is identified by a unique four-digit number. A computer file linking the unique number with the subject's name will be kept on a stand-alone, password-protected computer. All data requiring hand entry (e.g., cardiovascular measures) will be entered by two separate staff members and comparison macros will be run to ensure accuracy. Data files for experimental tasks and physiological measures from each experimental session will be manipulated and combined into a single electronic spreadsheet for each subject by one of the investigators. Data for all subjects will then be combined into a single electronic spreadsheet and separated by experimental measure for statistical analysis using SPSS (IBM, Armonk, NY).

In this protocol the primary outcome measure will be the influence of PHEN maintenance on the reinforcing effects of COC. The alpha level will be set at 5%.

As noted above, wherever possible, data are collected using an automated computer system, which increases the accuracy and completeness of data collection and ensures the validity and integrity of the data. The initial data manipulation described above will be conducted twice and compared. The quality of manipulated data and data analyses will be monitored by random inspection by the PI and/or Co-Investigators.

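### PHEN order is counterbalanced over two maintenance blocks, but the primary ANOVA has no period term, so any shift between blocks inflates the error of the PHEN main effect

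*Combined protocol and SAP*

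**What the plan says.** Section 3 (Study Design) states: "A double-blind, placebo-controlled, crossover design will be used in this experiment". Section 7 (Research Procedures) says under General Procedures that "order of PHEN dosing will be counterbalanced across subjects", and repeats under Drug Dose and Administration that "PHEN doses will be given in counterbalanced order across subjects".

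Table 1 in section 7 sets out two consecutive maintenance blocks, days 3-17 and 18-32. The four COC sessions of each block fall on days 14-17 and 29-32. The table prints one sequence only, starting with "Placebo maintenance. Placebo administered twice daily (0700 and 1900 hours"; read with the text, it is one of two orders.

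Under Data Analysis in section 7, break point and number of COC doses earned "will be analyzed with two-factor mixed-model ANOVA with COC" (four levels) and PHEN (two levels) as within-subject factors. Attenuation "will be inferred if the main effect of PHEN or the interaction of COC and PHEN attains statistical significance". No section supplies a period, sequence or order term.

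The error term for the PHEN test is not named. The only mention concerns Tukey's test after a significant interaction, where "the mean square error term will be used to conduct" the comparisons. The Data Monitoring Plan in section 17 says the data will be "separated by experimental measure for statistical analysis using SPSS", without naming a procedure.

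**The concern.** All COC sessions under one maintenance condition lie in one block, and those under the other condition lie in the other block. PHEN versus placebo is therefore a between-block comparison within each subject. If responding changes from the first block to the second for any reason other than PHEN, a subject who takes placebo first has that change added to the PHEN-placebo difference, and a subject who takes PHEN first has it subtracted.

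Counterbalancing cancels the change from the average when the two orders are equal in number. It does not remove it from the spread of the differences. A model without period counts that spread as error, so the PHEN main effect becomes harder to detect, although the block order of every subject is known.

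The number per order is not stated. Section 4 counts 36 completers, and section 7 provides for early termination, so the split among completers may differ from the split assigned. An unequal split would leave part of the block change in the PHEN estimate.

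**Working it through.** **Inputs from the documents (section 7, Data Analysis; section 17 for alpha).** N = 36, alpha 0.05, d = 0.44, stated power 0.80, four COC doses, two PHEN conditions.

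**Assumed, because the documents are silent.**
- Two-sided test, with d read as the standardised within-subject difference.
- A block shift π, constant over COC doses, of 0.25, 0.5 or 0.75 SD of that difference. The two larger values exceed the effect the trial is sized for and are upper cases.
- Two readings of the error term: (a) PHEN-by-subject, 35 df; (b) pooled residual with no PHEN-by-subject variance, 288 observations - 36 subjects - 7 effects = 245 df.

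**The plan's own figure.** A two-sided paired t test with n = 36 and d = 0.44 has power 0.728, not 0.80; one-sided it is 0.827. If d is scaled by the raw SD, with two measurements, 0.80 is reached at a correlation between 0.5 (0.73) and 0.6 (0.82). The G*Power test and correlation are not given, so the figure is neither confirmed nor refuted. The baseline of 0.73 below comes from the reading of d, not from period. Only the comparison with and without period matters here.

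**Model.** With SD 1, the subject difference D has mean τ + π in one order and τ - π in the other. With n1 and n2 subjects per order, the mean of D is τ + b, where b = π(n1 - n2)/36.
- *Without period:* the error sum of squares is noncentral chi-square on 35 or 245 df, with noncentrality 36π² - 36b². Rejection probability follows by numerical integration.
- *With period:* the estimate is the average of the two order means, with standard error ½√(1/n1 + 1/n2) and 34 or 244 df. Power comes from the noncentral t.

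**Loss at 18:18 (b = 0).** The standard error without period grows by √(1 + 36π²/df). For π = 0.5 under (a) this is √(1 + 9/35) = 1.12, an effective sample of 36/1.257, about 29.

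| π (SD) | (a) power | (b) power | (a) type I | (b) type I |
|---|---|---|---|---|
| 0 | 0.728 | 0.749 | 0.050 | 0.050 |
| 0.25 | 0.707 | 0.746 | 0.044 | 0.049 |
| 0.5 | 0.643 | 0.737 | 0.029 | 0.046 |
| 0.75 | 0.540 | 0.722 | 0.015 | 0.042 |
| any, with period | 0.727 | 0.749 | 0.050 | 0.050 |

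**The full decision rule.** The COC-by-PHEN test is a second route to the conclusion. It is unaffected by a constant shift under (a) and slightly conservative under (b) (0.048, 0.043, 0.037). A 40,000-run simulation of the either-test rule for one outcome at 18:18 assumed equal attenuation at 20, 40 and 80 mg and none at 0 mg. Power at the three shifts is 0.77, 0.72, 0.64 against 0.79 with period under (a), and 0.80, 0.79, 0.77 against 0.80 under (b).

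**Unequal completers (assumed splits).** At 22:14 and π = 0.5, b = 0.5 × 8/36 = 0.11 SD. Type I error of the PHEN test without period, at π = 0.25, 0.5 and 0.75:

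| Split | (a) | (b) |
|---|---|---|
| 20:16 | 0.046, 0.038, 0.027 | 0.052, 0.058, 0.067 |
| 21:15 | 0.050, 0.049, 0.045 | 0.056, 0.074, 0.101 |
| 22:14 | 0.055, 0.065, 0.073 | 0.062, 0.096, 0.151 |

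With period in the model it is 0.05 throughout.

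**The case against.** The strongest reply is that the harm is hypothetical. No document suggests a block shift of any given size, and several features favour a small one: a practice session, acclimation to the unit, about 11 days of maintenance before sessions and the same inpatient routine in both blocks. At 0.25 SD and equal orders the loss is 2.1 points under PHEN-by-subject error and 0.3 under a pooled residual; at 0.1 SD the first figure is about 0.3. At equal orders the planned test is also unbiased and conservative, and the interaction test offers another route. The clearest type I inflation needs an uneven split, a large shift and pooled error together. Since the target is 36 completers, replacement might keep the orders balanced.

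All of this stands as a limit on the size of the problem. It does not restore the missing term. Practice and acclimation do not address the effect of four earlier COC sessions on the second block. The plan does not choose the pooled residual, under which the loss is small. If PHEN response varies between subjects, pooling raises type I error by itself (0.09 to 0.175 at zero shift in the cases simulated).

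One further limit also stands. A single period effect removes only a shift that is constant over COC doses. It does not remove carryover, or a shift that depends on dose or on which condition came first.

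**Conclusion.** The concern holds. The omission is certain, but its cost cannot be fixed from the documents. For shifts from 0 to 0.75 SD at equal orders, the PHEN test loses between 0 and about 19 power points under PHEN-by-subject error (0.727 - 0.540), and between 0 and 2.6 under a pooled residual. There is no bias at 18:18, only lost precision. Bias of π(n1 - n2)/36 arises if completers are unequal by order. These sizes rest on the assumed shifts and splits, the reading of d as a paired standardised difference, and a shift additive over COC doses. The change should be made, with medium confidence in its practical importance: the remedy is nearly free, and it protects a test that can carry the primary conclusion alone.

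**What to change.** In section 7, Data Analysis, add period (first or second maintenance block) as a fixed effect to the COC-by-PHEN models for break point and number of COC doses earned, and to the peak-effect and AUC models. Name the error term used for the PHEN test. Report completers per PHEN order. Label Table 1 as one of the two PHEN orders. The period effect can be estimated only if both orders are used, as the text states; if placebo always came first, it would coincide with PHEN.

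The cost is one line of analysis text, one table label and one error degree of freedom, with no new data. If there is in fact no shift, the power given up at d = 0.44 under PHEN-by-subject error is about 0.1 point at 18:18, 0.6 at 20:16, 1.3 at 21:15 and 2.2 at 22:14. With a pooled residual it is under 0.1, 0.5, 1.2 and 2.2 points.
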